8.4 Serious Adverse Event Reporting

In case of a serious adverse event (whether or not related to the investigational device), or an unanticipated adverse device effect, the investigator should complete the applicable SAE eCRF pages within 24 hours. If the eCRF cannot be completed within 24 hours, the investigator should advise the Sponsor by other means, within 24 hours.

The Sponsor or designates such as the CRO will assist the site with reporting any SAEs to the reviewing ethics committee, according to their requirements and timelines.

In addition, an independent medical advisor will review safety related aspects of the investigation including review of serious adverse events (SAEs) and unanticipated adverse device effects. The medical advisor will be an independent physician not participating as a clinical investigator in the clinical trial who will provide safety oversight for the investigation. For sites in Australia, the Local Sponsor, Five Corners, is responsible for notifying the Therapeutic Goods Administration (TGA) within 7 calendar days of being made aware of all fatal or life threatening, serious and unexpected adverse device events, and within 15 calendar days of being made aware of all other USADEs, with a copy to Applaud Medical Inc.

All SAEs and UADEs must be reported to and reviewed by sponsor and designee as per the table above:

1) Five Corners

Email: [contact]

2) Applaud Clinical Affairs:

Applaud Medical, Inc.

Email: [contact]

NOTE: As applicable, reports must identify participants using the study's unique identifier to protect study participant's confidentiality.

9. MONITORING

Applaud Medical, Inc. or its designee may meet with the investigator prior to the initiation of the study in order to review the adequacy of patient population, facilities, and equipment with respect to the needs of the study, and familiarize investigator with the study protocol.

Applaud Medical, Inc. or its designee will periodically review the data to ensure that the study investigator is in compliance with the protocol and the investigators agreement. Applaud Inc. or its designee will monitor the site to ensure that the completed eCRFs match the medical records and raise queries in the database of any differences.

Applaud Medical, Inc. or designee may meet with investigator at the time enrollment is initiated in order to ensure that the participants are being properly selected, that the methods described in the study are thoroughly understood by the investigator, and that study data are being correctly recorded.

Applaud Medical, Inc. or its designee may visit the clinical site anytime during the course of the study. Additionally, telephone consultation will occur as necessary during the course of the study investigation to ensure proper progress and documentation of the study findings.

10. STATEMENT of COMPLIANCE

An investigator shall conduct the investigation in accordance with the signed agreement with the sponsor, the protocol, local regulations, and any conditions of approval imposed by the ethics committee.

The investigation will be conducted in compliance with the ethical principles that have their origin in the Helsinki Declaration. The investigation will also be conducted in compliance with the Clinical Investigational Plan (CIP), Good Clinical Practice and protection of human participants (21CFR50), ISO 14155: 2011, and regulations of participating countries.

The clinical investigation shall not begin until the required favourable opinion has been obtained from the Ethics Committees, and regulatory authorities. Any additional requirements imposed by the Ethics Committees, IRBs and regulatory authorities shall be followed.

In addition, the principal investigator shall

- a) indicate his/her acceptance of the CIP in writing,
- b) conduct the clinical investigation in compliance with the CIP,
- c) create and maintain source documents throughout the clinical investigation and make them available as requested during monitoring visits or audits,
- d) ensure that the investigational device is used solely by authorized users, and in accordance with the CIP and instructions for use,
- e) propose to the sponsor any appropriate modification(s) of the CIP or investigational device or of the use of the investigational device
- f) refrain from implementing any modifications to the CIP without agreement from the sponsor, Ethics Committee and regulatory authorities, if required,
- g) document and explain any deviation from the approved CIP that occurred during the course of the clinical investigation,
- h) ensure that an adequate investigation site team and facilities exist and are maintained and documented during the clinical investigation,
- i) ensure that maintenance and calibration of the equipment relevant for the assessment of the clinical investigation is appropriately performed and documented, where applicable,
- j) ensure the accuracy, completeness, and timeliness of the data reported to the sponsor in the eCRFs and in all required reports,
- k) maintain the device accountability records,
- l) allow and support the sponsor to perform monitoring and auditing activities,
- m) be accessible to the monitor and respond to questions during monitoring visits,
- n) allow and support regulatory authorities and the EC when performing auditing activities,
- o) ensure that all clinical-investigation-related records are retained as specified in Section 7.4 of ISO 14155:2011, and
- p) sign the clinical investigation report.

10.1 Protocol Deviations

The investigator agrees to conduct the investigation in accordance with this protocol. An investigator may not deviate from this Clinical Investigation Plan without first receiving approval in writing from the sponsor and EC, except when necessary to eliminate apparent immediate hazards to a participant.

Deviations will be documented on eCRFs. Investigators will also adhere to procedures for reporting investigation deviations to their EC in accordance with their specific EC reporting policies and procedures.

11. STATISTICAL METHODS

11.1 Population to be analysed

Primary analyses of study data will include available data on all enrolled participants, referred to in International Conference on Harmonization document E9 (“Statistical Principles for Clinical Trials”) as the full analysis set. Study enrollment is defined as that time when the participant signs the informed consent form and is then eligible to begin screening assessments. Other study participants will be classified as screen failures.

Study analyses will then be conducted on two distinct cohorts of study participants: an intent-to-treat (ITT) analysis including all enrolled participants and all available data, and a per-protocol (PP) analysis including the subgroup meeting all inclusion and exclusion criteria and for whom treatment was performed according to the study protocol with follow-up through 30 days (or 14 days if no follow-up imaging was required beyond 14 days). Both ITT and PP analyses will be summarized and reported.

11.2 General Considerations

Standard summary statistics will be calculated and reported; for continuous variables, statistics will include means, standard deviations, medians and interquartile ranges. Categorical variables will be summarized as frequencies and percentages.

All p-values will be two-sided, with values less than 0.05 deemed significant.

All statistical analyses will be performed using SAS (version 9.4 or higher, SAS Institute Inc. Cary, NC), R (version 3.2 or higher, R Foundation for Statistical Computing, Vienna, Austria) or other widely accepted statistical or graphical software.

11.3 Primary Endpoint

The study’s primary endpoint is treatment success, which is the proportion of study participants who are successfully treated following up to 2 ELS treatments. This is defined as absence of stones or with remaining fragments of less than 3 mm on the largest dimension by follow-up imaging through 30 day visit after last ELS procedure. If ELS Treatment was performed on two stones in one participant, both stones/fragments need to meet the endpoint to be counted as a success.

The study will test the statistical hypothesis that the treatment success rate is not inferior to the performance goal defined using published AUA treatment guidance (64%). Formally, the null and alternative hypotheses are as follows:

$$H_0: p < PG$$

$$H_A: p > PG$$

where p is the success rate observed in the prospective study outcomes and PG is the performance goal. The PG in turn is computed as:

$$PG = r - p - \Delta,$$

where r is the reference rate, p is a correction for differences in treatment success definitions and Δ is the statistical testing margin. These values are further defined as follows:

- $r = 64\% = 0.64$ is the reference rate derived from AUA guidance [13]
- $p = 4\% = 0.04$ is a correction factor for the difference between the definition of treatment success in the literature reference and the definition in the study protocol. Specifically, the reference rate is measured after any number of treatments, while the investigational protocol permits at most two treatments before treatment effectiveness is measured.
- $\Delta = 10\% = 0.10$ is the statistical testing margin for comparison.

Hence $PG = r - p - \Delta = 64\% - 4\% - 10\% = 50\% = 0.50$ in the primary endpoint hypothesis testing. The hypothesis test will be performed by comparing the observed success rate to the PG via exact binomial methods, where a lower two-sided 95% exact confidence bound exceeding the PG will constitute rejection of the null hypothesis.

11.4 Secondary Endpoints

The study's secondary endpoints are listed in Section 5.2.

These endpoints, as well as any additional endpoints defined *a priori* in the study protocol or analyzed *post hoc*, will be tabulated and reported descriptively using summary statistics as cited in section 11.2.

Summary tables and listings will be provided for all reported adverse events, as classified by MedDRA system organ class and preferred term, and additionally categorized by seriousness and relatedness. Such summaries will be comprised of the number and percentage of subjects with an adverse event and the total number of such events.

Additionally, a line-item listing of all reported adverse events will be provided.

11.5 Handling of Missing Data

Primary analyses will consist of all available data on enrolled participants, as stated above. Consequently, data will only be absent from analyses of study outcomes in the event that they were not available for collection. Replacement of data via methods such as multiple imputation may be employed when summarizing and reporting study outcomes.

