4.5 Participant Withdrawal or Discontinuation

Study participants may withdraw from the study at any time at their request and may also be discontinued at the physician's discretion or for other event/s related to the participant's health or welfare, including study participants' non-compliance with pre-study requirements. Participation in the study will cease immediately if the study participant requests to be terminated from the study.

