11.6 Sample Size and Power

Sample size and power are predicated on hypothesis testing of the primary endpoint and computed from the *a priori* hypothesis testing previously specified.

- Reference rate: 64%
- Performance Goal = 50% = 0.50
- Estimated ELS performance of 68%

- Desired power: 80%

The required evaluable sample size for a two-sided test at standard alpha of 0.05 was then derived in SAS version 9.4 (SAS Institute, Cary, NC, USA) and found to be 58. Assuming an attrition rate of 30%, 75 patients will be enrolled.

At this planned sample size, the minimal observed success rate required under the above assumptions is 64% (37/58), for which the lower two-sided 95% exact confidence limit is 0.502, just exceeding the PG of 0.50.

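### The primary analysis is available-case under an ITT label, with no binding rule for treated participants whose outcome is missing

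*Combined protocol and SAP*

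**What the plan says.** Section 11.1 equates the full analysis set with all enrolled participants and plans "an intent-to-treat (ITT) analysis including all enrolled participants and all available data", alongside a per-protocol analysis. Section 11.5 repeats that primary analyses use available data, so that "data will only be absent from analyses of study outcomes in the event that they were not available for collection". It then adds: "Replacement of data via methods such as multiple imputation may be employed when summarizing and reporting study outcomes". It gives no imputation model, no condition for using one, and no statement of whether it would be primary or supportive.

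The endpoint (Sections 5.1 and 11.3) is judged on imaging up to and including the 30-day visit after the last ELS procedure. Section 6.2.5 schedules imaging at Day 14, and Section 6.2.6 schedules CT at Day 30. Section 6.4 has non-ELS interventions on the treated stone recorded on an eCRF but does not link them to the endpoint. Section 6.3.1 has the investigator document why an eligible participant is not retreated. On withdrawal, Section 4.5 says: "Participation in the study will cease immediately if the study participant requests to be terminated from the study".

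The synopsis and Section 11.6 plan up to 75 enrolled for about 58 evaluable. Section 11.7 promises a separate SAP with further detail.

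**The concern.** An intention-to-treat label suggests that everyone treated is accounted for. Here the denominator is everyone whose outcome happened to be collected. In a single-arm study judged by one comparison with a fixed goal, no control group absorbs selective loss, so any link between missing outcomes and failure goes straight into the result.

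Such a link is plausible. Participants whose stone persists are the ones with a reason to decline retreatment, seek another procedure or withdraw. Section 2.2 describes the study as confirmatory and intended for marketing applications, so a success claim that depends on who came back for imaging would be open to challenge.

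**Working it through.** **Inputs.** Section 11.2: "All p-values will be two-sided, with values less than 0.05 deemed significant". Section 11.3 sets the decision rule: "where a lower two-sided 95% exact confidence bound exceeding the PG will constitute rejection of the null hypothesis". Section 11.6: "Performance Goal = 50% = 0.50"; it also gives assumed ELS success of 68%, desired power of 80%, 58 evaluable, 75 enrolled and a minimum pass of 37/58.

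**Reproducing the plan's figures.** Normal approximation with the null variance under the null hypothesis:

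n = [(1.96 × √(0.5 × 0.5) + 0.842 × √(0.68 × 0.32)) / 0.18]² = 58.1.

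The exact (Clopper-Pearson) lower limit is 0.484 for 36/58 and 0.501 for 37/58, so 37 is the pass mark (the protocol prints 0.502; the difference is immaterial). With X binomial on 58, P(X ≥ 37) is 0.0240 at 50% success and 0.7975 at 68%. The nominal false-success rate is therefore 2.4%.

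**How many could be missing.** 75 − 58 = 17, and 17/75 = 22.7%. Section 11.6 states 30% attrition, which would leave 75 × 0.70 = 52.5 evaluable. Neither figure is a rate among treated participants, because Section 4.4.4 places enrollment at consent, before screening. The number treated but missing is thus unknown, and 17 is an upper planning figure.

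**Effect of selective loss.** Let m treated participants be missing with success rate q, 58 be analysed, and true success among all treated be 50%. Then

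analysed rate = [0.5 × (58 + m) − m × q] / 58, and false success = P(X ≥ 37) on 58 at that rate.

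For example, m = 10 and q = 20% gives (34 − 2)/58 = 0.552. Each cell shows the analysed rate, then false success:

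| Treated but missing (m) | q = 40% | q = 20% | q = 0% |
|---|---|---|---|
| 5 | 0.509; 3.2% | 0.526; 5.7% | 0.543; 9.3% |
| 10 | 0.517; 4.3% | 0.552; 11.7% | 0.586; 25% |
| 17 | 0.529; 6.3% | 0.588; 26% | 0.647; 61% |

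At a true rate of 50%, q = 40% means failures go missing 60/40 = 1.5 times as often as successes, q = 20% means 80/20 = 4 times, and q = 0% means only failures go missing. These values of m and q are assumptions.

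**Cross-check with a random number missing.** Take 75 treated, each with an average 22.7% chance of being missing, and a pass mark that follows the number analysed. False success is 1.85% if loss is unrelated to outcome; it is 5.0%, 8.9% and 16.5% if failures are lost 1.5, 2 and 3 times as often as successes.

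**Why missing-as-failure should not be the primary rule.** With 17 treated and missing, the pass mark is 47/75 (lower limit 0.507), so 47 of the 58 observed (81%) must succeed. At 68% true success, P(X ≥ 47) on 58 is 2.0%. As a sensitivity analysis it is informative: after 37/58, 47 − 37 = 10 of the 17 would have to be successes for the result to stand.

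**The case against.** The strongest reply is that many participants with uncleared stones will have an outcome. Because the endpoint uses imaging up to the 30-day visit and Day 14 imaging is scheduled, someone who shows residual stone of 3 mm or more at Day 14 and then leaves can be read as an observed failure. A reader might infer that everyone who goes on to another procedure falls out of the denominator. The documents do not say that, and Section 4.5 ends participation without discarding data already collected. What stands is that no section says how these participants count.

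A reader might also take all 17 as treated dropouts and quote 26% or 61% as the type I error. The documents support neither step: some of the 17 may be untreated screen failures, whose exclusion does not bias success among the treated, and those two figures need steep dependence of loss on failure. The lower cells of the table are equally compatible with the plan.

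It is also true that one extra failure turns 37/58 into 37/59 (lower limit 0.491, a fail). Nearly any result exactly at a threshold behaves this way, so it shows fragility and not bias.

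Finally, the separate SAP may settle the matter before outcomes are seen. Its content and timing are not visible here, so the inference that the imputation choice will be made after the result is known is unsupported. The protocol nevertheless commits that SAP to no missing-outcome rule, and Section 11.5 already defines the primary analysis.

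**Conclusion.** The point holds as a gap in pre-specification that can bias the only confirmatory test. As written, treated participants without usable imaging after ELS are dropped, imputation is discretionary, and the handling of non-ELS intervention and of early departure with residual stone is undefined. The direction of bias is upward whenever uncleared participants are missing more often; that condition is plausible but is not shown by the documents. The size is uncertain: false success runs from about 3% (5 missing, mild dependence) to 61% (17 missing, all failures), against a nominal 2.4%. Confidence is high that the rule is absent and moderate on how much it matters. It should be fixed before outcome data are reviewed, because the study rests on a single pass/fail comparison.

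**What to change.** Amend Section 11.5, and carry the same text into the SAP, as follows.

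- **Denominator:** all participants in whom a first ELS treatment was started. Untreated screen failures are then excluded explicitly.
- **Observed failures:** residual fragments of 3 mm or more on the last imaging after ELS, or a non-ELS intervention on the treated stone before the endpoint was met.
- **No usable imaging:** one multiple imputation model, fixed before outcome data are reviewed, using stone size, location and any Day 14 result (for instance, from the first treatment when imaging after the second is absent).
- **Sensitivity analyses:** missing-as-failure, and the number of missing participants who would have to be successes for the conclusion to stand. Neither should be primary, for the power reason shown above.
- **Reporting:** the counts consented, screen-failed, treated, and treated but missing, with reasons.

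The cost is protocol and SAP wording and a little extra programming. The reported success rate and the power may be somewhat lower than under the available-case rule. Some participants counted as failures at Day 14 might have cleared by Day 30, so the rule leans conservative for those who leave early. The power of the revised rule should be checked once a rate of missing outcomes among treated participants has been assumed.

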11.6 Sample Size and Power

Sample size and power are predicated on hypothesis testing of the primary endpoint and computed from the *a priori* hypothesis testing previously specified.

- Reference rate: 64%
- Performance Goal = 50% = 0.50
- Estimated ELS performance of 68%

- Desired power: 80%

The required evaluable sample size for a two-sided test at standard alpha of 0.05 was then derived in SAS version 9.4 (SAS Institute, Cary, NC, USA) and found to be 58. Assuming an attrition rate of 30%, 75 patients will be enrolled.

At this planned sample size, the minimal observed success rate required under the above assumptions is 64% (37/58), for which the lower two-sided 95% exact confidence limit is 0.502, just exceeding the PG of 0.50.

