	
9. Participant has planned general anesthesia during index procedure with American Society of Anesthesiologists (ASA) physical classification level of 3 or greater
 
10. Known sensitivity to possible medications used before, during, or after the ELS procedure, including but not limited to the following: sedative agents, general anaesthetics, topical anaesthetics, and opioid analgesics
 
11. Coagulation abnormality or taking prescription anticoagulants that cannot be stopped during treatment. Aspirin usage will be discontinued at least 7 days prior to enrollment at the discretion of the attending physician
 
12. Mobility issues - unable to comfortably lie still for up to 120 minutes or unable to roll from back to side
 
13. Known hypersensitivity to conductivity gel
 
14. Body mass index (BMI) ≥ 35 unless anticipated skin to stone distance (anticipated distance from site of ELS treatment head to stone per pre-operative CT) is < 135 mm
 
15. Implanted spinal cord neurostimulator intrathecal pump or any device that may interfere with energy transmission
 
16. Participant has open wounds, lesions, dermatitis, or ischemic tissues in the treatment area
 
17. Participant has had a major surgery that removed tissue around the spinal cord (e.g. a laminectomy) within the treatment area
 
18. Participant will undergo treatment of a stone located in the distal ureter and has previous hernia repair or surgical mesh implanted in the inguinal/hypogastric regions

Sample Size	Up to 75 participants will be enrolled to achieve approximately 58 participants that are evaluable for the primary endpoint
Enrollment period/Timeline	February 2019 through January 2020 (11 months)
Number of sites	Up to eight sites. Participating countries include Australia and New Zealand
Follow-up Schedule and Study Procedures	
Participants require follow-up through 90 (± 21) days after their last ELS procedure with interim visits at Day 1, 2, 3, 7 (± 1), 14 (± 4) and 30 (± 4) days
 
Pre-procedure testing (minimum):
 
 a. Urinalysis b. Urine culture c. Serum creatinine d. Computed Tomography (CT) scan (non-contrast) within the last 14 days showing location, radiodensity and size of stone e. Assessment of pain medication intake f. Pain assessment g. An x-ray KUB is recommended if participant is suspected to have radiolucent stones and CT scout film is not available or suitable for use

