4.4.4 Point of enrollment

Enrollment is defined as that time when the participant signs the informed consent form and is then eligible to begin screening assessments. Participants who fail to meet screening assessment requirements (see Section 6.1) will be counted as a screen failure and will not be treated with the ELS. Screen failures will be documented at the site on a screening log.

Each enrolled study participant will be assigned a unique participant identification number at the time of enrollment. This participant identification number will be retained throughout the study. Investigational site will keep a log that notes the participant's name and corresponding participant identification number. All electronic case report forms (eCRFs) will be tracked, evaluated, and stored using only the participant ID number. No personal identifying information will be included on the eCRFs.

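### Enrolling 75 with 30% attrition leaves about 52 evaluable participants, not 58, so the stated 80% power becomes about 68–71%

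*Combined protocol and SAP*

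**What the plan says.** Section 11.6 sets out the design inputs: "Performance Goal = 50% = 0.50", "Estimated ELS performance of 68"% and "Desired power: 80"%. It then reports an evaluable sample size of 58 and moves to enrolment in one sentence: "Assuming an attrition rate of 30%, 75 patients will be enrolled". It also gives 37 of 58 as the smallest number of successes that would meet the goal.

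The synopsis gives the same pair of numbers without an attrition rate: "Up to 75 participants will be enrolled to achieve approximately 58 participants that are evaluable for the primary endpoint". Section 4.2 repeats that 75 is the upper limit.

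Section 11.3 fixes the decision rule as an exact binomial comparison, "where a lower two-sided 95% exact confidence bound exceeding the PG will constitute rejection of the null hypothesis".

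Section 4.4.4 determines who counts towards the 75: "Enrollment is defined as that time when the participant signs the informed consent form and is then eligible to begin screening assessments". Those who then fail screening are not treated.

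**The concern.** An attrition rate is normally the fraction of enrolled participants lost, so the evaluable number is enrolled × (1 − attrition). On that reading, 30% attrition, 75 enrolled and 58 evaluable cannot all be true. No definition of attrition in the documents reconciles them.

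The study is described as confirmatory, is meant to support premarket applications, and rests on a single primary hypothesis test. Its evaluable size, its power and its quoted success count all refer to 58. If the plan's own attrition occurs, the trial ends with five or six fewer evaluable participants and a larger chance of missing its goal when the device performs as assumed. Because 75 is a ceiling, the text leaves no room to recruit more.

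**Working it through.** **Inputs.** Null rate 0.50, true rate 0.68, two-sided alpha 0.05, target power 80%, 58 evaluable, 30% attrition and 75 enrolled (all Section 11.6). The decision rule is that the lower limit of the two-sided 95% exact interval exceeds 0.50 (Section 11.3).

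**Step 1: reproduce the 58.** The one-sample normal approximation is

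n = [(1.960 × √(0.50 × 0.50) + 0.842 × √(0.68 × 0.32)) / (0.68 − 0.50)]² = 58.1.

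With the exact rule at n = 58, 37 successes are needed. One-sided alpha is 0.0240 and power at 0.68 is 79.8%. The 58, the 37/58 and the 80% are therefore sound. The exact lower limit for 37/58 computes to 0.501, where Section 11.6 prints 0.502; the decision is unaffected.

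**Step 2: the enrolment step.**

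- Correct inflation: 58 / (1 − 0.30) = 82.9, so 83.
- Adding 30% to the evaluable number: 58 × 1.30 = 75.4, which matches the printed 75.
- Evaluable after 30% attrition from 75: 75 × 0.70 = 52.5.
- Attrition that 75 and 58 imply: (75 − 58) / 75 = 17/75 = 22.7%.

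**Step 3: exact power at the size the plan would reach.** For each n, find the smallest count whose lower exact 95% limit exceeds 0.50, then take the binomial probability of that count or more at a true rate of 0.68.

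| Evaluable n | Successes needed | Observed rate | Lower limit | Power |
|---|---|---|---|---|
| 58 | 37 | 63.8% | 0.501 | 79.8% |
| 53 | 35 | 66.0% | 0.517 | 68.0% |
| 52 | 34 | 65.4% | 0.509 | 71.4% |

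Exact power moves in a sawtooth as n changes: 74.7% at 51, 74.5% at 54, 77.2% at 56. To avoid depending on how 52.5 is rounded, let each of 75 participants be retained independently with probability 0.70. Average power is then 71.5%, and the chance of reaching 58 or more evaluable is about 10%.

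**Step 4: screen failures (assumed rates, one reading only).** The documents give no screen-failure rate. If 10% or 20% of the 75 consents failed screening and 30% of the remainder were then lost, the evaluable number would be 75 × 0.90 × 0.70 = 47 or 75 × 0.80 × 0.70 = 42. Power would be 68.1% (31 of 47 needed) or 64.3% (28 of 42 needed). The main result does not use these figures.

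**The case against.** Several points can be made for the plan.

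- **The sawtooth exaggerates the loss.** 58 is a local peak of exact power and 53 a local trough. Averaging over a binomial evaluable number on both sides, 75 enrolled gives 71.5% and 83 enrolled gives 76.1%, a difference of about 4.6 points. This stands as a caution against reading the 68% literally, and it shows that even 83 would not secure a full 80% once the evaluable number is allowed to vary. It does not restore the 80%: the average from 75 stays near 71%.
- **The 30% may be a mislabelled over-enrolment allowance.** 17/58 is 29%, and the synopsis pair is coherent by itself at 22.7% loss. This is plausible, but the text calls it attrition, and a reader cannot tell which figure was intended.
- **Attrition may already include screen failures**, since enrolment is counted at consent. That is fair, and it is why Step 4 is kept apart from the main result.
- **The analysed number could exceed the evaluable number.** Section 11.1 analyses all enrolled participants and Section 11.5 permits imputation. But imputation is optional, primary analyses use available data, and Section 11.6 powers the study on evaluable participants.
- **Validity is untouched.** The exact interval and type I error hold at any realised n, and Section 11.3 already supplies the success rule for any n. That is correct. The defect lies in the planning figures, not in the test.

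**Conclusion.** The concern holds. The 58 is right for its inputs, but 75 enrolled does not deliver it at 30% attrition. The plan would reach about 52 evaluable participants, with exact power of 71.4% at 52, 68.0% at 53 and 71.5% on average. Against the 79.8% at 58, that is a loss of about 8 to 12 points; the chance of missing the goal with a device that truly achieves 68% rises from about 20% to about 29%.

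This rests on attrition meaning the share of enrolled participants not evaluable, on its reaching the assumed 30%, and on the plan's true rate of 0.68. At 22.7% attrition or less, 75 still gives 58.

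**What to change.** Make Section 11.6 and the synopsis agree, by one of these routes:

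1. **Keep 75 and 58.** Replace 30% with the attrition that these numbers support, 22.7% (17 of 75), and say why that rate is realistic. The synopsis can stay as it is.
2. **Keep 75 and 30%.** Restate the plan as 52 evaluable, at least 34 of 52 successes and power of about 71%, and change the synopsis to match.
3. **Keep 58 and 30%.** Raise the cap to 83 in the synopsis, Section 4.2 and Section 11.6.

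Under any route, say whether attrition includes screen failures, given that enrolment is counted at consent; if it does not, the enrolment figure needs a separate allowance. Mark 37/58 as the threshold at 58 only. It must not be carried over as a 64% cut-off: 34 of 53 is 64.2%, yet 35 would be needed. The rule in Section 11.3 already governs any realised n and needs no change.

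Routes 1 and 2 cost only wording, plus a lower stated attrition or a less favourable stated power. Route 3 costs 83 − 75 = 8 more participants.
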